2.0 OBJECTIVES AND SCIENTIFIC AIMS

Aim 1: Evaluate the efficacy of ERT-C versus CBT-C in improving caregiver primary outcomes (i.e., anxiety and depression symptoms as assessed via the HADS, PSWQ and RRS), caregiver secondary outcomes (i.e., quality of life, burden), and cancer patient outcomes (i.e., patient quality of life, perceived stress, healthcare service utilization), above the effects of varying sites and stages of cancer.

- *Hypothesis 1a:* ERT-C as compared to CBT-C will result in greater improvements in caregiver primary and secondary outcomes and these gains will be maintained up to 6-months follow-up.
- *Hypothesis 1b:* ERT-C will lead to greater improvements in cancer patient outcomes as compared to CBT-C at 3-months follow-up.
- *Exploratory Hypothesis 1c:* Assess putative moderators (cancer site, cancer stage, and caregiver sociodemographic factors) of the efficacy of ERT-C versus CBT-C.

Aim 2: Evaluate the impact of gains in adaptive emotion regulation skills (e.g., attention regulation, metacognitive regulation assessed via the ACS, EQ-D and ERQ-R) in improving caregiver primary and secondary outcomes.

- *Hypothesis 2a:* Only skills that specifically target components of distress (i.e., attention regulation, metacognitive regulation) will mediate primary and secondary caregiver outcomes compared to other facets of improving the caregiving experience (i.e., reducing perceived burden, maladaptive behavioral coping).
- *Hypothesis 2b:* These gains and mediation in attention and metacognitive regulation will be more pronounced in caregivers receiving ERT-C as compared to CBT-C.

Aim 3: Examine treatment linked changes in salivary markers of stress for caregivers (e.g., diurnal cortisol) and inflammation (e.g., Interleukin 6).

- *Hypothesis 3a:* ERT-C will result in greater reductions in cortisol dysregulation and systemic inflammation as compared to CBT-C, and these gains will be maintained at 6-months follow-up.
- *Exploratory Hypothesis 3b:* Reductions in cortisol dysregulation and systemic inflammation observed with ERT-C will be most prominent in caregivers with baseline elevations in distress.

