leads to maladaptive behavioral responses, which, over time can lead to biological dysregulation and dysfunctional threat and reward learning. This progression feeds back to influence more rigid processing of new emotional events in caregiving. The caregiver context

is not especially modifiable, as most caregivers do not feel that they have choice over this role and often feel a concurrent sense of obligation, which together results in internal distress. Distress reflects the temporal internal processing of a situation in which the caregiver has difficulty focusing away from potential threats and losses and struggles to gain perspective to balance caregiving and everyday life (i.e., attentional rigidity¹⁰⁹⁻¹¹¹). In turn, distressed caregivers have difficulty reappraising threat and loss appraisals and often become caught in perseverative negative thinking, including worry and rumination,¹⁶ self-criticism,¹⁷ and loneliness.^{18,19} Reliable patterns of neural activation¹¹² and neurophysiological systems^{18,20} are associated with worry and rumination, and these processes exert considerable impact on cognitive functioning, role functioning,¹¹³ and treatment prognosis.¹¹⁴ Because of this internal distress, caregivers often turn towards maladaptive coping (e.g., excessive drinking, unhealthy eating) which further increases the bodily stress response and, over time, as a

whole, increases markers of prolonged stress (e.g., chronic inflammation, dysregulated cortisol levels).^{71,74,115-119} Serum markers of inflammation covary with adaptive and maladaptive emotion regulation strategies.¹²⁰ Evidence for these dysfunctional temporal progressions is supported by experimental and longitudinal findings in distress disorders.¹²¹⁻¹²⁵

Figure 1
Emotion Regulation Therapy to Address Caregiver Distress.

With this model as a frame, treatment can be specified to target each component of the caregiver context with particular attention to internal distress (See Figure 1, Panel C). Many

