ERT has been adapted for caregivers through a two-phase process.¹³⁰ First, the content and format of the ERT manual was modified to produce an 8-session intervention. Next, an abbreviated Delphi Method helped further refine the manual content; six caregivers reviewed the manual and were interviewed to provide feedback, and the revised manual was subsequently re-sent to the same six caregivers for further review and final feedback. This process produced an caregiver-focused streamlined version of ERT (ERT-C)^{130,131} sensitive to caregiving demands and barriers to psychosocial service use among caregivers.^{48,92,132} This consolidated version requires less intense time-commitment and integrates the key ERT approaches to addressing the components of distress (see C.2.3 for a detailed description of ERT-C). As illustrated in Figure 1, Panel C, ERT-C targets the emotional trajectory of the caregiver context through 1) increasing motivational awareness to make clearer and more intentional choices in caregiver-related situations, despite not being able to change the situation, 2) increasing attention regulation ability to promote more flexible attention in the face of increasing internal distress related to the caregiver context; 3) training in metacognitive regulation to increase perspective taking (i.e., decentering) and reframing of this internal distress towards greater courage and compassion; and 4) improved ability to respond to emotional activation

by directly impacting the bodily responses to emotions (i.e., response modulation). Over time, repeated engagement of caregiver-related emotional scenarios with this alternative approach will lead to broader and more varied learning related to meaningful rewards and a sense of safety, as well as normalization of biological stress pathways in immunological and endocrine functioning.

Empirical Support for the Efficacy and Neurobehavioral Mechanistic Findings for ERT.

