11.0 EVALUATION DURING TREATMENT/INTERVENTION

MEASURE/TEST	Time to complete	Intervention Sessions (ERT-C or CBT-C) ^a	T2 (1-wk post last ERT-C or CBT-C) ^{b, e}	T3 (3-mos post ERT-C or CBT-C) ^e		T4 (6-mos post ERT-C or CBT-C) ^e
				Caregiver	Pt	
		Caregiver Only	Caregiver Only	Caregiver	Pt	Caregiver Only
Distress Thermometer (DT)	2 min	X	X	X		X
Hospital Anxiety and Depression Scale (HADS)	5 min	X	X	X		X
Penn State Worry Questionnaire (PSWQ)	5 min		X	X		X
Rumination-Reflection Questionnaire, Rumination subscale (RRQ-R)	5 min		X	X		X
Attentional Control Scale (ACS)	5 min	X	X	X		X
Experiences Questionnaire, Decentering subscale (EQ-D)	5 min	X	X	X		X
Emotion Regulation Questionnaire, Reappraisal subscale (ERQ-R)	3 min	X	X	X		X

Caregiver Quality of Life Index-Cancer (CQOLC) ^f	5 min		X	X		X
Caregiver Reaction Assessment (CRA) ^f	5 min		X	X		X
Self-Administered Comorbidity Questionnaire (SCQ)	5 min		X	X		X
Patient-Reported Outcomes Measurement Information System Global Health Scale (PROMIS-GH)	4 min		X	X	X	X
Credibility and Expectancy Questionnaire (CEQ)	2 min		X			
EORTC QLQ-C30	3 min				X	
Perceived Stress Scale (PSS)	4 min				X	
National Survey on Drug Use and Health (NSDUH), Healthcare Utilization	2 min				X	
Working Alliance Inventory-Short Form (WAI-SF)	8 min	X ^c				
COPE, Active Coping Subscale	2 min.	X				
Inflammatory Markers Assessment	5 min		X	X		X
Diurnal Cortisol Assessment	2 min. 4x a day over 3 days		X ^d	X		X
Total Time		22 min	80 min	78 min	13 min	78 min

^a ERT-C or CBT-C will be delivered over 8 individual sessions by a trained study therapist. The 8 sessions must be completed within 8 to 16 weeks from initiation of the first session. ^b Questionnaires at T2 should be completed on the same day as the last session, but may be completed within 1 week. ^c The Working Alliance Inventory will be administered after the fourth intervention session. ^d Saliva collection at T2 should begin the day after the last session. ^e Training case participants will not be asked to complete follow-up assessments. ^f Bereaved caregivers who report their loved one passing away will not be asked to complete these assessments.

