Power and Sample Size for Aim 2. Statistical power for mediation models was estimated from simulations by Fritz and MacKinnon, [202] which provide conservative estimates given the reduction in noise provided by our weekly assessments and growth curve modeling. Allowing for up to 20% attrition, the sample will provide at least 80% power to detect mediation using the Sobel test if one of the two paths (α or β) has a small-medium effect size (Cohen's $d=0.39$), and the other has at least a small effect ($d=0.26$).

Aim 3: Differential Effects of Treatment on Change in Biomarkers. We will describe and test differential changes in inflammation and salivary biomarkers overall and by treatment arm.

Hypothesis 3a: ERT-C will result in greater reductions in cortisol dysregulation and systemic inflammation as compared to CBT-C and gains will be maintained at 6-months follow-up.

Exploratory Hypothesis 3b: Reductions in cortisol dysregulation and systemic inflammation observed with ERT-C will be most prominent in caregivers with baseline elevations in distress.

Primary Analyses: The same HLM/GLIMMIX framework from Aim 1 will be used for Aim 3. Transformations may be needed for both biomarkers. The analysis will be similarly conducted to assess both differential pre-post change (T1 to T2) and also maintenance at 6-months follow-up (T2 to T4), using appropriate contrasts on the time variable. This same framework will allow for testing the exploratory moderation hypothesis. Specifically, for Hypothesis 3b, outcomes will be regressed on the ERT-C indicator, an indicator of elevated baseline distress, and the interaction of the two. A significant finding on the interaction term will be evidence to a moderation effect and will be followed with stratified analyses of the biomarker outcomes by baseline distress category and treatment arm.

Power and Sample Size for Aim 3. Based on previous participation rates with biological samples at our institutions, we anticipate at least 75% of the 240 enrolled caregivers to provide samples. With a conservative 20% attrition assumption, an analytic sample of $n=144$ would provide 80% power to detect a small-medium effect size of $d=0.36$ for the t-test for Hypothesis 3a.

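### No prespecified contrast estimates the ERT-C versus CBT-C difference in biomarker change from baseline to 6 months, although Hypothesis 3a claims a benefit that lasts to that point

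*Combined protocol and SAP*

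**What the plan says.** **Hypothesis.** Section 2.0 states that "ERT-C will result in greater reductions in cortisol dysregulation and systemic inflammation as compared to CBT-C". Section 14.0 repeats the comparison and ends it "as compared to CBT-C and gains will be maintained at 6-months follow-up". The claim has two parts: a gain, and its presence at 6 months.

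**Analysis.** Section 14.0 (Aim 3, Primary Analyses) takes over the Aim 1 mixed-model framework and will "assess both differential pre-post change (T1 to T2) and also maintenance at 6-months follow-up (T2 to T4), using appropriate contrasts on the time variable". The Aim 1 text in the same section speaks of obtaining several comparisons as contrasts in one framework. It then restricts the immediate-gain model to T1–T2 and the maintenance model to post-intervention data. The change scores to T2, T3 and T4 described there serve the exploratory Aim 1 moderator analysis, not Hypothesis 3a.

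**Timing.** Section 3.0 places biological change late in the treatment model: "Over time, repeated engagement of caregiver-related emotional scenarios with this alternative approach will lead to broader and more varied learning", and the same sentence ends "as well as normalization of biological stress pathways in immunological and endocrine functioning". It describes the harmful process in similar terms: maladaptive responses "which, over time can lead to biological dysregulation and dysfunctional threat and reward learning". Neither statement gives weeks or months. Section 11.0, footnote d, sets the first post-treatment sample: "Saliva collection at T2 should begin the day after the last session". T4 is 6 months after that session.

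**The concern.** The quantity that answers the 6-month part of Hypothesis 3a is the arm difference in change from T1 to T4. Neither named contrast is that quantity. With two separately restricted models, fitted to different sets of participants once there are missing samples, their two estimates need not even add up to it.

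Two things follow. First, a finding of maintenance would rest on a non-significant T2 to T4 difference, which is compatible with losing much of the gain. Second, if part of the ERT-C advantage appears after T2, each planned test sees only a piece of it. A trial with a real difference at 6 months could then report two non-significant results. A T1 to T4 contrast chosen after seeing those results would look post hoc, although the samples needed for it are collected anyway.

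**Working it through.** **Inputs from the documents.** 240 caregivers, 1:1 allocation, 75% providing samples, 20% attrition (Section 14.0). Sessions are completed in 8–16 weeks, and T4 is 6 months, about 26 weeks, after the last session (Section 4.1).

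**Assumptions.** Two-sided 0.05 (no alpha is stated for Aim 3), effects in SDs of the change score, and the same change-score SD for every pair of visits. Effect timing is varied because the documents do not give it.

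**The plan's own figure.** 240 × 0.75 × 0.80 = 144, or 72 per arm, which reproduces. For a two-sample t-test the noncentrality is d × √(72/2) = 6d, with 142 degrees of freedom. At the stated d = 0.36 this gives 57% power, not the stated 80%. At n = 144, 80% power needs d = 0.47. That discrepancy is a separate matter. Here d = 0.47 is used as the total effect at T4, so that the T1 to T4 contrast has 80% power by construction.

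**Splitting the effect.** If a share f is present at T2, the T1–T2 effect is 0.47f and the T2–T4 effect is 0.47(1 − f). Linear accrual from session 1 gives f = 8/34 = 0.24 to 16/42 = 0.38. Larger shares represent earlier effects. With equal change-score SDs the two contrasts share the T2 measurement with opposite signs, so they correlate at −0.5. The chance that either is significant in favour of ERT-C was simulated with a large-sample normal approximation; using the t critical value lowers it by about one point.

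| Share at T2 | d, T1–T2 | d, T2–T4 | Power T1–T2 | Power T2–T4 | Either | T1–T4 |
|---|---|---|---|---|---|---|
| 24% | 0.11 | 0.36 | 10% | 57% | 65% | 80% |
| 38% | 0.18 | 0.29 | 19% | 41% | 57% | 80% |
| 50% | 0.235 | 0.235 | 29% | 29% | 55% | 80% |
| 70% | 0.33 | 0.14 | 50% | 13% | 61% | 80% |
| 80% | 0.38 | 0.09 | 61% | 9% | 68% | 80% |
| 100% | 0.47 | 0 | 80% | 5% | 82% | 80% |

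**Sensitivity to correlation.** Under AR(1) with a monthly correlation of 0.90–0.95 (an assumption) and linear accrual, change over a short interval is less variable. With 12 weeks of treatment, T1–T2 has 27–30% power and T2–T4 has 59–62%. Over 8–16 weeks either test succeeds in about 70–76%, against 80% for T1–T4.

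**Maintenance.** Suppose d = 0.47 is reached at T2 and half is then lost. The T2–T4 difference is 0.235, its power is 29%, and it is non-significant about 71% of the time. The standard error of an arm contrast is √(2/72) = 0.167, so a 95% CI for the T1–T4 difference has a half-width of 1.98 × 0.167 = 0.33. That interval is wide, but it is centred on the benefit that remains.

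**The case against.** The strongest reply concerns timing. A reader might infer that the protocol's own theory predicts slow biological change, and that the plan therefore tests at the wrong time. The documents do not support this. Section 3.0 gives no time scale, and 8–16 weeks of sessions with practice between them also fits. Hypothesis 3a presupposes a gain that is then held. The pilot in Section 3.0 reports inflammation reductions of 2% to 33% from pre- to post-treatment in 15 caregivers. By Section 4.2, attention and metacognitive skills are taught in sessions 1–4 and applied in sessions 5–7, so they have been in use before T2. The low T1–T2 power figures therefore belong to one scenario, not to the protocol.

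A reader might also infer that a late benefit goes untested, or would be reported as nothing to maintain. That is wrong too. The Aim 1 text reads the follow-up interaction as a different change between arms and allows for further separation after treatment, so a T2–T4 difference would be seen.

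Nor can T1–T4 replace T2–T4, because it can be significant after much of the T2 gain has gone.

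Two smaller points also stand. T1–T4 may have fewer than 72 per arm (with 64, taken as an illustration, its power is 75%). Aim 3 is described as exploring biomarkers and lies outside the four primary outcomes. The wording about contrasts would permit a T1–T4 comparison, but permitting one does not prespecify it.

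**Conclusion.** The gap is a fact of the text: no prespecified contrast estimates the 6-month biomarker benefit that Hypothesis 3a claims, and the maintenance model leaves baseline out. That a non-significant T2–T4 result cannot establish a remaining benefit does not depend on any theory of slow change.

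The loss of power does depend on the scenario. It is roughly 12 to 25 percentage points (80% against 55–68%) when 24–80% of a d = 0.47 effect is present at T2. This assumes 72 per arm, two-sided 0.05 and equal change-score SDs. It is roughly 4 to 10 points under the AR(1) assumption with linear accrual, and nil if the whole effect is present at T2.

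A reader might also infer that the Aim 1 superiority rule, which needs a significant T1–T2 result, would block any 6-month finding. Section 14.0 carries over the modelling framework to Aim 3 but does not say that the rule goes with it, so the plan should settle this. The point is a worthwhile correction to a non-primary aim and does not threaten the trial's main conclusions.

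**What to change.** In Section 14.0, Aim 3 Primary Analyses:

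- Fit one mixed model per biomarker to T1–T4, including every caregiver with any sample.
- Keep the T1–T2 and T2–T4 contrasts, the latter to describe maintenance or further change.
- Add a prespecified arm difference in change from T1 to T4, with its 95% CI, as the estimate of the 6-month benefit in Hypothesis 3a.
- State that a T1–T4 difference will be reported as a 6-month benefit whether or not T1–T2 is significant, and that non-significance of T2–T4 alone will not be read as maintenance.
- State the alpha for Aim 3.

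The cost is wording and one more contrast per biomarker, with no new samples or visits. Section 9.0 names three inflammatory markers and four cortisol indices, so this means at least 3 + 4 = 7 additional contrasts if all are tested. They should be counted in any multiplicity handling for the aim.

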4.0 OVERVIEW OF STUDY DESIGN/INTERVENTION

4.1 Design

This study is a randomized, controlled trial to determine the efficacy of ERT-C vs. CBT-C in improving anxiety and depression symptoms, worry and rumination (primary outcomes), and caregiver and patient QOL (secondary outcomes) in distressed caregivers of/and patients with varying sites and stages of cancer (Aim 1), evaluate whether gains in emotion regulation ability and dysfunction reflect mechanisms underlying therapeutic change (Aim 2), and explore whether ERT-C is associated with reductions in biological markers of stress and inflammation (Aim 3). Participants will be 240 caregivers of patients with any site or stage of cancer who are currently receiving medical care of any kind (e.g., curative, palliative) at MSK (n=130) or MGH (n=110) who will be randomized 1:1 into ERT-C or CBT-C. We also strive to collect data from the 240 patients for whom enrolled caregivers provide care, though caregiver participation is not contingent on patient participation. 1-2 training cases per ERT interventionist will also be enrolled on this study for training purposes. Training case participants will only receive the treatment sessions and will not be asked to complete study assessments.

Potential participants will be screened for eligibility. After consenting to the study, caregiver and patient participants will complete baseline assessments (T1) (Appendix H and Appendix I). Caregivers for whom the patient does not consent to enroll are still eligible for inclusion. Caregivers will additionally provide saliva samples to measure inflammatory markers and cortisol levels (details of collection method provided below). Training case participants will not complete baseline assessments.

Caregivers will be randomly assigned to ERT-C or CBT-C and will meet with the therapist one-on-one via telepsychiatry (e.g., Webex, Zoom, Teams) for 8 individual sessions to be completed within 8 to 16 weeks from initiation of the first session. Each session is 60 minutes in length and will be audio and video recorded (e.g. Webex, Zoom, Teams) for MSK participants. Sessions will only be audio recorded (e.g. Zoom, handheld recorders) for MGH participants. With the participant's consent, session recordings may be used for academic, educational, or training purposes. This will happen when a session is particularly compelling or represents a noteworthy example of ERT-C or CBT-C in practice. Before each treatment session (but same day as treatment session), caregivers will complete a brief assessment of emotion regulation skills (weekly measures, Appendix H). After the fourth session (mid-point of intervention), caregivers will also complete a measure of therapeutic alliance.

Within 1 week of the last ERT-C or CBT-C session, caregiver participants will complete the second assessment (T2) and saliva samples to measure inflammatory markers and cortisol levels. Additionally, caregivers will complete the third assessment and saliva samples to measure inflammatory markers and cortisol levels (T3) at 3 months (+/- 1 week) following completion of the last session, and the fourth assessment and saliva samples to measure inflammatory markers and cortisol levels (T4) at 6 months (+/- 1 week) following completion of the last session. Training case participants will not complete T2, T3, or T4 assessments.

Caregiver participants who become bereaved while on study will be given the option to withdraw or remain on study. Assessments for bereaved caregivers will not include the

Caregiver Quality of Life Index-Cancer (CQOLC) or the Caregiver Reaction Assessment (CRA). Patient participants will complete baseline assessments (T1) and at 3-months following caregiver completion of ERT-C or CBT-C (T3) (Appendix I).

Participant Reimbursement: Caregiver participants will be reimbursed for their time for participating at each timepoint (e.g. electronic gift cards, gift cards, money orders, etc). Reimbursement is structured such that each subsequent timepoint is reimbursed at a higher rate to encourage continued participation:

(T1) Baseline (T1) = \$5

(T2) Post-treatment assessment = \$10

(T3) 3-month follow-up (after ERT-C/CBT-C last session) = \$15

(T4) 6-month follow-up (after ERT-C/CBT-C last session) = \$20

Caregiver participants will also receive \$10 at the completion of each ERT-C or CBT-C session. Caregivers who complete the entire study (i.e., all 8 sessions and all 4 timepoints) will receive \$130/participant. Patients will be compensated \$25 after the completion of their T3 assessment.

The research team will give the participant a research study receipt (Appendix J) at each timepoint.

Training case participants will not receive compensation.

Biospecimen Collection:

To evaluate inflammatory markers, caregiver participants will provide an oral mucosal transudate (OMT) sample to be collected using the OraSure collection device. MSK staff will mail MSK participants an OraSure collection device, shipping materials, collection diary (Appendix K), a copy of the slides from the instructional video (Appendix N), and a cover letter (Appendix L), MGH staff mail the same materials to participants at MGH and include an intervention-specific welcome sheet at T1 collection (Appendix MGH-H, MGH-I). The research team will email participants with an expected delivery date, a link to an instructional video, and a brief summary of the contents and description of the box. At T1 collection, the package will also include a workbook corresponding to the intervention the participant was randomized to receive (Appendix C, W).

To evaluate diurnal cortisol, caregiver participants will provide saliva samples over three days at each major timepoint. Caregivers will be instructed to swab for 2 minutes and then to remove the pad from the mouth and place it directly in the vial containing an aqueous antimicrobial preservative solution. Caregivers will collect saliva samples upon awakening, 30 minutes later, 8 hours later, and at bedtime.¹⁴⁹ Participants will be instructed to go about their normal daily activities on data collection days and will complete a diary to assess relevant health behaviors (e.g., caffeine, tobacco, and alcohol consumption; physical activity, sleep) and daily stress. To avoid sample contamination, caregivers will be instructed to avoid brushing their teeth, eating, or drinking within 20 minutes pre-sampling (Appendix K, N).

Caregivers will be instructed to keep samples in the freezer prior to returning them to the research laboratory and to ship samples as soon as possible after the last collection day. The samples and the collection diary should be shipped using the shipping materials and return label provided to:

[name]
Program in Public Health
[name]
[name]
[name]

Samples will be shipped by secured mail and are stable at standard temperatures for up to 21 days from collection. At-Home Saliva collection distribution and mailing details are included in Appendix M.

If a participant reports receiving the COVID-19 vaccine while on study, the study team will document the date of vaccination receipt. If the date of vaccination fall within 7 days of a biospecimen collection timepoint window, the participant will be instructed to not collect any samples until 7 days have passed since their vaccination. If a participant reports a COVID-19 diagnosis at any collection point, the study team will document this and instruct them not to collect biospecimens.

Training case participants will not provide biospecimen collection.

Consultant and Collaborator Roles

The research team will be led by Drs. [name] and [name] and brings together research leaders in Emotion Regulation Therapy (Drs. [name], [name], and [name]), Cognitive Behavioral Therapy (Drs. [name] and [name]), psychoneuroimmunologic correlates of distress ([name]), and biostatistics ([name]). Study implementation will also rely on support roles including a Clinical Research Coordinator and Clinical Research Supervisor.

